We confirmed that the BMS-984923 does not affect glutamate/DHPG-induced Ca^{2+} signaling in mGluR5-overexpressing HEK-293T cells and extended these observations to DIV21 cortical neurons (Figure 3A) (Haas 2017). In contrast, a NAM, MTEP, strongly suppresses glutamate/DHPG-induced Ca^{2+} responses. Co-application of BMS-984923 and MTEP prevents MTEP-induced inhibition of glutamate/DHPG-induced Ca^{2+} responses (Figure 3A) (Haas 2017). This confirms that the BMS-984923 behaves as silent allosteric modulator of mGluR5, consistent with competition at the MTEP site.

BMS-984923 has good oral bioavailability and an apparently linear dose response (Figure 2B). At 7.5 or 15 mg/kg, plasma concentration exceeds 2 μM at 10 h. Brain concentrations are nearly as high 3 hours after a 7.5 mg/kg oral dose (Figure 2C). Compounds chemically related to the BMS-984923, but with PAM activity, induce seizures (Compound 5 of (Yang 2016)). To determine whether the BMS-984923 compound at the 7.5 mg/kg dose occupies brain mGluR5, we assessed the degree to which BMS-984923 prevented PAM-induced seizures (Haas 2017). During the 90 min after PAM administration, 50% of vehicle-pretreated mice exhibited seizures, whereas none of the SAM-pretreated mice did so (Haas 2017). Thus, the SAM effectively occupies brain mGluR5 sites to prevent PAM action. Based on the BMS-984923 pharmacokinetics, brain penetration and potency for mGluR5, we chose the BMS-984923 dose of 3.75 mg/kg by oral gavage twice a day as the dose to ensure essentially complete continuous receptor occupancy.

It is known that higher doses of mGluR5 NAMs such as MTEP negatively affect EEG amplitude in mice (Um 2013). At 15 mg/kg/d B.I.D., MTEP is tolerated in mice, and has been applied successfully to recover AD-like phenotypes in transgenic mice (Um 2013). However, we observed that a 5-fold increased dose of MTEP (75 mg/kg) strongly impairs EEG amplitude and alters the power spectrum in mice (Haas 2017), demonstrating MTEP's limited therapeutic window. In contrast, neither a 1x dose (3.75 mg/kg) nor a 10x dose (37.5 mg/kg) of BMS-984923 impairs EEG amplitude or power spectrum in mice (Haas 2017). Thus, doses of SAM BMS-984923 well above the effective dose appear to be well tolerated with regard to CNS function in mice.

Protection from $\text{A}\beta$ o action by BMS-984923

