
10. **Risks:** Describe the reasonably foreseeable risks, including risks to subject privacy, discomforts, or inconveniences associated with subjects participating in the research.

Risks Associated with BMS-984923

BMS-984923 has not previously been administered to humans. Toxicology studies have been completed in rat and non-human primate, with no adverse effects at the doses comparable to the planned doses. At doses higher than those planned for this study in humans [see Investigator Brochure (IB) section 4.3.2.1], serious adverse effects related to drug accumulation were observed in rats receiving repeated doses greater than 15 mg/kg/day. These adverse effects were gradual in onset over days and were manifest by lethargy, generalized stress responses, and death without organ specific or acute toxicity. This constellation of serious adverse effects was reversed after cessation of daily 100 mg/kg/day administration. There was no evidence for acute onset cardio-respiratory or CNS toxic effects. In order to mitigate the risk of similar adverse effects in humans, our planned maximal dose is well below the human equivalent of the rat and monkey no observed adverse effect level (NOAEL). Please refer to the Investigator Brochure (IB) for more detailed information on toxicology investigations.

Risks Associated with Electrocardiograms (ECGs)

There is no pain or discomfort during an ECG; however, removing the pads may cause some irritation to the skin.

Risks Associated with Blood Drawing and IV Line Insertion

Drawing blood and inserting an intravenous line (IV) into an arm vein are safe and standard medical procedures. Sometimes a bruise will occur at the puncture site and rarely a blood clot or infection will occur in the vein. Certain individuals may feel light-headed during venipuncture. A total of approximately 70 mL (~5 tablespoons) of blood will be collected from each participant during this study. A total of approximately 140 mL (~10 tablespoons) of blood will be collected from each participant in Cohort 4 and subsequent dose cohorts.

Psychological Stress

The tests used to assess the participant's mental performance may sometimes cause anxiety or fatigue.

Risks Associated with Unanticipated Events

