The PI and medical monitor may elect to stop dosing or stop the study based on any treatment emergent concerns. Although not expected based on animal toxicology and PK studies, participants will be monitored for clinically significant neuropsychiatric symptoms with the GDS and NPI-Q, neurological symptoms by exam, cognitive toxicity with testing, and laboratory abnormalities. While the planned doses are below the human equivalent of the repeated doses which caused serious adverse effects with lethargy in rat, participants will be monitored by frequent repeated GCS observations. Dosing may be stopped due to the occurrence of any individual adverse events which, in the judgment of the PI and medical monitor, need further characterization with respect to progression and reversibility before further dosing is conducted. Such adverse events may include non-serious unusual events. If dosing is stopped, review of the data by the medical monitor and DSMB must occur with a positive recommendation before dosing can be resumed.

Attribution of Adverse Events

- Definite: Adverse event(s) will clearly be related to investigational agent or other intervention and cannot be reasonably explained by an alternative explanation – i.e., concomitant drug(s), concomitant disease(s). The relationship in time is very suggestive.
- Probable: Adverse event(s) will likely be related to investigational agent. The relationship in time is suggestive that the adverse event is likely related to the investigational agent. An alternative explanation is less likely – i.e., concomitant drug(s), concomitant disease(s).
- Possible: Adverse event(s) may be related to investigational agent. An alternative explanation – i.e., concomitant drug(s), concomitant disease(s), - is inconclusive. The relationship in time is reasonable; therefore, the causal relationship cannot be excluded.
- Unlikely: Adverse event(s) will doubtfully be related to investigational agent(s). An adverse event for which an alternative explanation is more likely – i.e., concomitant drug(s), concomitant disease(s), and/or the relationship in time suggests that a causal relationship is unlikely.
- Unrelated: Adverse event(s) will clearly not be related to the investigational agent

Plan for Grading Adverse Events

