Merely repeating an abnormal test, in the absence of any of the above conditions, does not constitute an AE. Any abnormal test result that is determined to be an error does not require reporting as an AE.

Adverse Events of Special Interest (AESI)

No Adverse Events of Special Interest (AESI) for this study have been identified in non-clinical toxicology studies with BMS-984923. Based on drug mechanism of action, the following are considered AESI for this study: central nervous system complications.

Plans for Reporting Adverse Events and Serious Adverse Events

The PI and research staff will monitor the study procedures for this trial for overall safety and scientific relevance on an ongoing basis. [name] (in conjunction with the medical monitor and DSMB as necessary) will evaluate every adverse event for safety and causality, and will determine whether the adverse event affects the Risk/Benefit ratio of the study and whether modifications to the protocol or consent form are required.

The PI will report the following types of adverse events to the Yale University HIC, DSMB, and IND holder within 48 hours of it becoming known to the investigator: a) all serious adverse events; b) non-serious adverse events occurring with a greater magnitude or frequency than expected; and c) other unanticipated problems involving risks to participants or others.

All adverse events post administration of a PET tracer will be reported to the PET center, the PET authorized user, and the YNHH RSC.

SAEs as defined in the HIC DSMP will be reported to the HIC, DSMB, and IND holder within 48 hours (using HIC Form 6A). In this report, the PI will give a brief description of the SAE including severity, duration, action taken, outcome, and plan. He will also give an opinion regarding the relationship of the SAE to the study drug and determine whether or not the protocol or consent form needs to be modified as a result of the SAE. If available, a report from the DSMB will accompany the HIC report submission. Reporting will not be delayed pending resolution or outcome of an event. If an outcome for an adverse event is not available at the time of the initial report, participant follow-up will proceed until such time as an outcome is known. A progress report of the study that includes all of the SAEs will be reported to the HIC in an annual request for renewal.

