No inferential statistical testing is planned. However, if used for exploratory analysis, inferences will be assessed against a 5% alpha, and therefore p-values ≤ 0.05 will be considered statistically significant. All tests will be two-sided. No adjustment will be made to p-values for multiple testing.

Participant Disposition and Exposure

The numbers of participants completing or withdrawing, along with reasons for withdrawal, will be summarized by dose.

Tabulation of the number of doses of study drug, duration of treatment as well as total dose given will be provided.

Demographics and Baseline Characteristics Analyses

Demographic variables (age, sex, race, and ethnicity) as well as height (cm), weight (kg), Body Mass Index (BMI), temperature, heart rate, blood pressure and respiratory rate or pulse oximetry (from the vital signs) at baseline will be summarized using descriptive statistics. All demographic data will be provided in a data listing.

Efficacy Endpoints

No efficacy endpoints will be assessed since this is a sample of healthy participants.

Safety Endpoints

The safety analysis will be descriptive in nature. All safety data will be listed, and data will be tabulated by dose. Safety data include:

- AEs
 - Events occurring prior to the first dose of study drug will be defined as pre- treatment events.
 - TEAEs will be defined as any AE occurring during or after oral administration of the study drug. Therefore, this will include all events occurring through Day 7/ET.

Incidence of AEs will be summarized for each cohort by MedDRA system organ class (SOC) and preferred term (PT), sorted in descending frequency by SOC, and then by PT within SOC. These summaries will be given by dose in separate tables for each of the following TEAE event sets:

- All events

- Treatment related events (defined by a relationship to study drug of possible, probable, or definite).
- Serious adverse events
- Events leading to premature discontinuation from study
- Events by maximum severity
- AEs of Special Interest, ie, events relating to cognitive decline or neuropsychiatric symptoms.

Other safety outcomes will include:

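### The AESI table in Section 13 is limited to cognitive and neuropsychiatric events, while Section 12 defines the AESI as central nervous system complications

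*Combined protocol and SAP*

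**What the plan says.** Section 12 (Data and Safety Monitoring Plan), under Adverse Events of Special Interest, says that toxicology identified none, and then sets the AESI from mechanism: "Based on drug mechanism of action, the following are considered AESI for this study: central nervous system complications". It gives no sub-list and no restriction.

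Section 13 (Statistical Considerations), under Safety Endpoints, lists the sets of treatment-emergent events to be tabulated by dose, by system organ class (SOC) and preferred term (PT). The sets are all events, related events, serious events, events leading to discontinuation, events by maximum severity, and "AEs of Special Interest, ie, events relating to cognitive decline or neuropsychiatric symptoms".

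On monitoring, Section 12 (Criteria for intervention discontinuation) says that "participants will be monitored for clinically significant neuropsychiatric symptoms with the GDS and NPI-Q, neurological symptoms by exam, cognitive toxicity with testing". It then adds a separate measure for lethargy. Recalling the rat findings, it states: "participants will be monitored by frequent repeated GCS observations".

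**The concern.** The two sections define the same prespecified safety set differently, and both are current text. In Section 13 the abbreviation *ie* makes the phrase a definition rather than a list of examples, so the table is restricted to what it names. No MedDRA term list or other rule connects the two.

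At stake is how the table is read. This is a first-in-human study with safety and tolerability in its primary objective. The AESI table is the only event set in Section 13 aimed at the central nervous system. A reader who takes the meaning of AESI from Section 12 could see no events in a cohort of six and conclude that there were no central nervous system complications, although somnolence or reduced consciousness had been recorded as an adverse event.

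**Working it through.** The plan gives no figure on this point and no arithmetic is needed beyond a count. The check sets the texts side by side.

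**Step 1: the central nervous system domains that the protocol monitors.** Sources are Section 4 (In-patient Treatment, Visit 2) and Section 12 (Criteria for intervention discontinuation).

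| Domain | How monitored | In the Section 12 AESI? | Named in the Section 13 AESI set? |
|---|---|---|---|
| Cognitive | Testing (MOCA) | Yes | Yes |
| Neuropsychiatric | GDS, NPI-Q | Yes | Yes |
| Neurological | Examination | Yes | No |
| Consciousness, lethargy | Repeated GCS | Yes | No |

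Section 13 names 2 of the 4.

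**Step 2: could neuropsychiatric be read to include the other two?** Not on the protocol's own usage. Section 4 assigns GCS to consciousness, and MOCA, GDS and NPI-Q to cognitive or psychiatric effects. Section 12 lists neuropsychiatric, neurological and cognitive findings as three items and gives lethargy its own instrument.

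**Step 3: what is the AESI label used for?** Section 12 attaches no reporting rule to it. The 48-hour list under Plans for Reporting covers serious events, non-serious events of greater magnitude or frequency than expected, and other unanticipated problems. The Section 13 table is thus the label's only stated use. If that table follows a narrower definition, the Section 12 definition has no stated effect for neurological and consciousness events.

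**Step 4: where else would these events appear?** They appear in the listings, in the all-events table by SOC and PT for each dose, and in the related, serious, discontinuation and severity tables where they qualify.

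**Step 5: are GCS scores summarised elsewhere?** The other safety outcomes in Section 13 name laboratory tests, vital signs, physical examination and ECG. GCS is not named. Only general wording covers it: safety data are to be listed and tabulated by dose, and remaining endpoints assessed according to their scale.

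**The case against.** The strongest reply is that little depends on this table. The SOC rows of the all-events table already group nervous system and psychiatric events by dose, so what is missing is one targeted set, not visibility. Escalation rests on all available clinical, safety and PK data. Any individual adverse event may stop dosing, and the DSMB reviews all non-serious events after each cohort. The analysis is descriptive, so no error rate or power is affected. All of this stands, and it limits the size of the point. It does not reconcile the two definitions.

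A second reply is that the lethargy evidence is weak as a basis for the AESI. The rat effects, "manifest by lethargy, generalized stress responses, and death without organ specific or acute toxicity", followed accumulation under repeated high doses. Section 10 reports no acute central nervous system toxicity, and Section 12 bases the AESI on mechanism. That is right. The point needs only that lethargy and consciousness are monitored as their own domain and fall within the Section 12 wording.

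A third reply is that Section 12 says complications, so not every minor event coded to the nervous system need count. This is fair, and is a reason to set the terms in advance.

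A reader might also infer that the table would hide a known seizure risk, since Section 3 says "Compounds chemically related to the BMS-984923, but with PAM activity, induce seizures". The documents do not support that. The statement concerns related compounds with a different activity, and in the same experiment BMS-984923 prevented those seizures.

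**Conclusion.** The inconsistency is real and should be corrected. Followed as written, Section 13 leaves out of the AESI table two of the four monitored central nervous system domains, both of which the Section 12 definition includes. The consequence is confined to the content and reading of one descriptive table.

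The conclusion rests on two readings: that *ie* defines the set, and that the unqualified Section 12 phrase covers neurological and consciousness-related events. Because no term list exists, a coder might still place lethargy under neuropsychiatric symptoms, but that would go against the protocol's own usage.

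Three stronger inferences do not hold. Events are not lost from safety reporting. The AESI table is not the only by-dose grouping of these events, because the SOC rows also group them. The defect cannot be expressed as a probability: the documents give no event rate, and the chance of seeing an event in six participants would describe how often events occur, not what the table omits.

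**What to change.** In Section 13, replace the *ie* clause with the Section 12 definition. The AESI table would then cover central nervous system complications, including neurological and consciousness-related treatment-emergent events as well as cognitive and neuropsychiatric ones. Set the MedDRA terms before analysis, for example from the nervous system and psychiatric SOCs, and tabulate by dose.

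Name a separate descriptive summary of GCS by dose. A GCS below 15 is a test finding, so count it as an AESI only when it meets the criteria for an adverse event under Abnormal Test Findings in Section 12.

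The cost is a wording change, a term list and one further descriptive summary from data already collected. The downside is a broader table that may include some minor nervous system events.

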This study is an open-label, single ascending dose study in healthy participants. Up to six cohorts of 6 participants each are planned where the participants within each cohort are expected to receive the same dose of study drug. A total of approximately 36 participants will be enrolled and each will receive a single dose of BMS-984923.

If the Maximum Tolerated Dose (MTD) is reached prior to the sixth cohort, the remaining participants may be enrolled to obtain further data at the tolerated dose levels. During this process, the Principal Investigator (PI) ([name]), the medical monitor, and the DSMB must agree to proceed with the study and escalate to the next dose cohort, independent of the influence of the IND holder ([name]) and in compliance with the management of the Conflict of Interest for [name]. The process is further described in Section 12 (Data and Safety Monitoring Plan). Briefly, a safety assessment will be completed and reviewed for all treated participants per cohort prior to opening enrollment into the next increased dose level.

The study periods protocol are as follows:

- **Screening:** (within 90 days prior to Day 1) Patients have 90 days from the time of signing informed consent to complete their screening assessments and, if needed, their washout period for prohibited concomitant medications. The screening laboratory tests must be completed within 30 days prior to Day 1.
- **Treatment period:** Day 1: Admission, administration of study drug, and 2 night in-patient stay; Day 3: Discharge following the completion of all scheduled procedures.

- **Follow-up:** Participants will have follow-up visits for up to 7 days post-dose as follows: Participants will return to clinic for visits on Study Days 4 and 7. Participants will receive a phone call on Study Day 5 to inquire about their general health.

Screening

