1994) will be administered prior to oral dose administration, again at approximately 6 hours post-dose (approximate peak concentration) and approximately 24 hours post-dose.

If a participant is found to be depressed, a clinician will perform further assessment and refer the participant to care as necessary. As part of ongoing adverse event monitoring, participants will be asked about changes in mood during in-person and phone visits. Additionally, they will be advised to call to inform the study team of changes in mood, specifically depression, between visits.

Blood will be collected for safety laboratory studies prior to drug dose administration and on Days 2 and 3. Safety laboratory studies will include a comprehensive metabolic panel [glucose, blood urea nitrogen (BUN), creatinine, sodium, potassium, chloride, bicarbonate, calcium, total protein, albumin, total bilirubin, alkaline phosphatase, aspartate transaminase (AST), alanine transaminase (ALT)], phosphate, a lipid panel [total cholesterol, low density lipoprotein (LDL), high density lipoprotein (HDL), triglycerides], a complete blood count and differential, lactate acid dehydrogenase (LDH), creatine kinase (CK), amylase, and a urinalysis with reflex microscopic examination.

Plasma will be collected for PK analysis as shown in [Table 4](#).

A 24-hour urine collection will be performed starting at the time of study drug administration. A second 24-hour urine collection will be performed from 24-48 hours after study drug administration. These samples will be used to measure urine drug and metabolite levels.

The participant will remain in the HRU on Study Days 1 and 2, and discharged on Study Day 3 after all required assessments have been completed. During the inpatient stay, abnormal assessments and laboratory values will be evaluated by the PI in collaboration with the medical monitor in real time. See the schedule of events ([Table 3](#)) for details on the assessments on each Study Day.

Post Treatment Follow-up Visits

See the schedule of events ([Table 3](#)) for details on the assessments on each Study Day.

Visit 3 (Day 4) – Vital signs (BP, pulse, respiratory rate, and oral body temperature) will be obtained. Plasma samples for PK assessments will be collected. Information on changes or newly administered concomitant medications as well as any new or ongoing (S)AEs will be collected at each visit.

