- Clinical laboratory tests presented as changes over time. Potentially clinically significant (PCS) ranges will be defined and used to determine the incidence of participants experiencing new-onset PCS laboratory values, where new-onset is defined as a PCS value for a participant following initiation of study treatment for which the participant did NOT have a PCS value for that analyte PRIOR to initiation of study treatment.
- Vital signs including: respiratory rate, heart rate, temperature, and blood pressure, as per the schedule of events. BMI will be assessed, with height collected only at screening.
- Physical examination
- 12-lead ECG. ECG parameters will be analyzed in a fashion similar to that of clinical laboratory parameters.

Concomitant treatments will be assessed according to the timing of their start/stop dates as they relate to the study drug treatment, as follows:

- Prior medications with start AND stop date before date of first dose of study drug.
- Concomitant medications with participant exposure that includes at least one dose of study drug.
- New-onset medications. Concomitant medications with a start date AFTER the first dose of study drug. New-onset medications are a subset of the full set of concomitant medications.

Changes from pre-treatment will be calculated in a similar fashion as for the efficacy endpoints, but no inferential statistics will be provided for safety endpoints. Shifts from baseline in ECG will be tabulated for heart rate and QTc. Other endpoints will be assessed according to the scale of the variable.

Pharmacokinetic Endpoints

Concentration data in plasma will be assessed descriptively over time. Correlation with safety and receptor occupancy outcomes may be performed, as the data warrant.

SECTION II: RESEARCH INVOLVING DRUGS, BIOLOGICS, RADIOTRACERS, PLACEBOS AND DEVICES

If this section (or one of its parts, A or B) is not applicable, check off N/A and delete the rest of the section.

A. RADIOTRACERS

N/A

1. Name of the radiotracer: $[^{18}\text{F}]$ FPEB
2. Is the radiotracer FDA approved? YES NO

If NO, an FDA issued IND is required for the investigational use unless RDRC assumes oversight.

3. Check one: IND# 150912

or RDRC oversight (RDRC approval will be required prior to use)

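### The new-onset PCS rule has no high/low direction, so an earlier abnormal value one way can remove a post-dose abnormal value the other way from the count

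*Combined protocol and SAP*

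**What the plan says.** Section 13, Safety Endpoints, lists the laboratory outputs as changes over time and an incidence of new-onset PCS values. The limits are left for later: "Potentially clinically significant (PCS) ranges will be defined and used". The counting rule is already fixed. It counts a PCS value after treatment starts only if it is one "for which the participant did NOT have a PCS value for that analyte PRIOR to initiation of study treatment". The rule mentions neither direction nor denominator. Under Analysis Populations, safety outcomes are assessed in everyone dosed.

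The extension to ECG is one sentence: "ECG parameters will be analyzed in a fashion similar to that of clinical laboratory parameters". Separately, "Shifts from baseline in ECG will be tabulated for heart rate and QTc".

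There are two scheduled laboratory draws before dosing. For the first, Section 4, Overall Study Design, says "The screening laboratory tests must be completed within 30 days prior to Day 1". For the second, the Visit 2 text says "Blood will be collected for safety laboratory studies prior to drug dose administration and on Days 2 and 3". ECGs are taken in triplicate at screening and again before dosing (Section 4, Screening Period, and Table 3, footnote 5).

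**The concern.** A new-onset table should show abnormalities that appeared after the drug was given. A participant whose value was too low before dosing and too high afterwards has a new abnormality, yet the rule treats it as pre-existing because the analyte is the same.

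Two further gaps follow from the wording. If a value was already PCS and then moves much further in the same direction, no PCS table picks this up. And if the denominator is everyone dosed, it includes participants who could not have been counted.

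All three effects push the reported incidence down. Safety is the primary objective, this is the first use of the drug in humans, and cohorts have six participants, so a single miscounted participant is visible in the table.

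**Working it through.** The plan gives no PCS limits and no expected PCS rates, so there is no stated figure to reproduce. The check has two parts.

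**1. The rule applied to single participants.** Take one analyte with both a high and a low PCS limit, in a cohort of 6, and count high values after dosing. For the written rule, assume the denominator is everyone dosed.

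| Pattern in the cohort | Written rule | Direction-specific rule with at-risk denominator |
|---|---|---|
| One participant low PCS before dosing, high PCS after | 0/6 = 0% | 1/6 = 16.7% |
| One participant high PCS before and after | 0/6 = 0% | 0/5 = 0%, with any worsening shown separately |
| One participant high PCS before and after; a different one newly high | 1/6 = 16.7% | 1/5 = 20.0% |
| No PCS value before dosing, one newly high | 1/6 = 16.7% | 1/6 = 16.7% |

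The first row is the direction fault, worth 16.7 points. The second and third rows show the denominator effect. The last row shows that nothing is lost when no earlier PCS value exists.

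**2. How often a participant is barred.** This is an illustration on assumed rates. Let *e* be the chance that one pre-dose value is PCS in a given direction, with the two draws independent. The written rule bars a participant if either draw is PCS in either direction: 1 − (1 − 2e)². A direction-specific rule that still looks at both draws gives 1 − (1 − e)².

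| e (assumed) | Written rule | Direction-specific | Difference |
|---|---|---|---|
| 0.5% | 1.99% | 1.00% | 0.99 points |
| 1% | 3.96% | 1.99% | 1.97 points |
| 2.5% | 9.75% | 4.94% | 4.81 points |
| 5% | 19.00% | 9.75% | 9.25 points |

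The chance that at least one of six participants is barred for that analyte is 1 − (1 − 2e)¹² under the written rule: 11.4%, 21.5%, 46.0% and 71.8% down the rows. The direction-specific rule, 1 − (1 − e)¹², gives 5.8%, 11.4%, 26.2% and 46.0%.

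Two draws from one person are unlikely to be independent. If they agreed completely, the shares would be 2e and e, for example 2.0% against 1.0% at e = 1%. Either way, ignoring direction about doubles the barred share.

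Being barred is not the same as losing an event: the participant must also have a post-dose PCS value. If a true share p has one and a share q of those is barred, the expected reported share is p(1 − q). With p = 2/6 = 33.3% and e = 1%, that is 33.3% × 0.9604 = 32.0% under the written rule and 33.3% × 0.9801 = 32.7% under the direction-specific one. At e = 5% it is 33.3% × 0.81 = 27.0% against 33.3% × 0.9025 = 30.1%. The average loss is modest, but within one cohort it comes in steps of 16.7 points.

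**The case against.** The best defence is that this is one descriptive table among several. Adverse events are tabulated by system organ class and preferred term, by relatedness and by severity. Laboratory changes over time, heart rate and QTc shifts and full listings do not depend on the rule. Section 8 excludes clinically significant screening laboratory abnormalities, which makes earlier PCS values less common. The limits are still to be set and could be written as separate high and low criteria. All of this stands and limits the size of the point. It does not remove it: the rule as worded still works per analyte, and under Section 12 an abnormal laboratory value becomes an adverse event only on certain conditions.

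A reader might infer more than the documents support:

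- *That laboratory and ECG safety incidence as a whole is understated, or that this is its only incidence summary.* Only the new-onset PCS count is affected, and adverse event incidence is also tabulated.
- *That a large share of participants loses events.* Taking 22 chemistry analytes and two draws, with 0.5% to 2% of values PCS and all independent, gives 1 − 0.995⁴⁴ = 20% to 1 − 0.98⁴⁴ = 59% of participants with some pre-dose PCS value. That is not a loss of events: the same analyte must be PCS again after dosing, and part of the figure is persistent same-direction abnormality, which is rightly left out.
- *That each hidden event is worth 1/5.* A participant hidden by an opposite-direction value is at risk and belongs in both numerator and denominator, giving 1/6. The 1/5 needs a different participant to be excluded.
- *That ECG triplicates give six chances to block.* The plan does not say that replicates are tested one by one.
- *That only the last pre-dose value should count.* With no reference arm, that choice would count a fluctuating pre-existing abnormality as new. Looking at all pre-dose values is defensible.
- *That same-direction values already PCS should enter the count.* Leaving them out is what new-onset means; what is missing is a place to show their worsening.

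**Conclusion.** The point holds in limited form. The rule as written may understate the new-onset PCS count for laboratory values and, by analogy, ECG parameters, because it ignores direction. It also leaves same-direction worsening without a PCS summary and states no denominator. One missed participant is 16.7 points in a cohort of six. The loss is zero where no participant has an earlier PCS value of that analyte, and the direction fault cannot arise for an analyte given only one limit. The barred shares in the working rest on assumed rates and show only the scale. No test, power figure or numerical escalation threshold depends on this count. It is still worth correcting: a stated rule that miscounts will be programmed as stated, and the repair costs almost nothing.

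**What to change.** Replace the new-onset definition with wording to this effect:

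> New-onset PCS is counted separately for the high and the low limit of each analyte. The denominator is participants with no PCS value in that direction before dosing. Participants already PCS in that direction are summarised in a separate table showing any worsening after dosing. As a sensitivity count, post-dose PCS values are also tabulated for participants who were PCS in that direction at screening but not at the Day 1 pre-dose draw. For ECG parameters the same rules apply to the mean of the triplicate at each time point.

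When the PCS limits are set, state which analytes have both a high and a low limit, and what size of change counts as worsening.

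No new data are needed. The cost is a short amendment to the analysis text and a little more table programming. Counts may look slightly less favourable, and the sensitivity count may include some abnormalities that come and go without the drug, which is why it stays apart from the main count.
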